1.4 Clinical Data to Date

The sponsor investigator completed a randomized placebo controlled trial of naltrexone as a therapy of patients with type 1 diabetes hypoglycemia unawareness in which 30 subjects enrolled over 3 years. One third were unable to complete the study: one because of rising liver function tests during the drug treatment and the rest for technical reasons related to the magnetic resonance imaging part of the study. In another study in which the default mode network was evaluated during hypoglycemia, we enrolled 11 people with type 1 diabetes and awareness of hypoglycemia, 9 people with type 1 diabetes and unawareness' of hypoglycemia, and 11 controls over an 18 months period. NAC has not been used in humans as a treatment of hypoglycemia unawareness in type 1 diabetes.

CONFIDENTIAL

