2.1 General Design

This is a single center, double blind randomized cross over design trial that will compare the impact of NAC vs. saline infusion during experimental hypoglycemia on day one on the responses to experimental hypoglycemia on day two. Figure 1 shows the protocol in schematic form. We intend to enroll 18 individuals to obtain the complete data sets from 15 participants.

Expected duration of subject participation is 10-12 weeks. This study will consist of a screening visit and two 2-day intervention visits separated by approximately 8 weeks.

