3.4 Early Withdrawal of Subjects

3.4.1 When and How to Withdraw Subjects

Subjects will be withdrawn at any point during the study if they remove their consent or if they develop any of the exclusion criteria after enrollment. In addition, any subjects who experience the symptoms of an allergic reaction to the NAC severe enough that the infusion is stopped early will be withdrawn from the study at the time the infusion is stopped (before unblinding that participant's treatment assignment). Procedures for withdrawal include collecting the necessary information to provide them with the compensation due them for the time they devoted to the study. At the end of the study, after treatment assignments are unblinded, a letter will be sent to the any subject withdrawn because of symptoms of an allergic reaction to NAC informing them of the treatment they were given. If they had been given NAC, we will instruct them to share the letter with their personal physician so the allergy could be noted in the clinical record.

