4.3 Method for Assigning Subjects to Treatment Groups

The investigational pharmacy at the University of Minnesota will be responsible for implementing the randomization order in which participants are given NAC or saline, prepared by the study statistician. This information will be blinded to investigators and participants and they will be unblinded only at the end of the study.

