7.5 Stopping Rules

Individuals will be withdrawn from the trial if they experience any symptoms of allergy to NAC severe enough to require early stopping of the infusion, including feeling itchy on their skin, having tingling or swelling in their mouth or tongue, or having trouble breathing.

A Data Safety Monitoring Board (DSMB) will be assembled at the start of the study to regularly monitor patient safety and study documentation of adverse and serious adverse events. This board will consist of the study statistician [name], endocrinologist [name] (who is independent of the study team), investigational pharmacist [name], and endocrinologist [name] (who is independent of the study team) from the University of Virginia. DSMB members will be unblinded to treatment assignments. They will review (1) incidence of early stopping of an infusion and (2) incidence of any adverse or serious adverse events on at least a monthly basis. After an experiment where the infusion was stopped early and an adverse or serious adverse event was reported, they will review that experiment's data within two weeks.

Participant accrual will be halted if an excessively high rate of participants with allergic symptoms requiring early stopping of the infusion is seen. Statistical sequential boundaries on the cumulative number of participants with allergic symptoms will be used to monitor the rate. If allergic symptoms requiring early stopping of the infusion are noted during an experiment, the participant will be withdrawn from the trial; the withdrawal will be carried out by blinded study staff, thus without knowledge of whether the infusion given was NAC or saline. The DSMB will then review the unblinded participant data within two weeks of the experiment. If the infusion given was saline, the reaction will be denoted in DSMB records as a placebo reaction, and that participant will not be counted towards the cumulative number of participants with allergic symptoms to NAC. If

CONFIDENTIAL

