the infusion given was NAC, and in the DSMB's judgment the reaction was likely related to NAC, then the reaction will be denoted in DSMB records as an allergic reaction to NAC, and that participant will be counted towards the cumulative number of participants with allergic symptoms to NAC. The DSMB will inform the PI that there was an allergic reaction to NAC, and at study's end the project PI will notify the participant that they should inform their personal care provider that an allergic reaction to NAC was observed.

Specifically, the trial will be stopped early if the number of participants with an allergic reaction to NAC is equal to or exceeds the boundary number (bn) out of n participants who have completed at least the Part 1 infusion (Table below). This is a Pocock-type stopping boundary that yields the probability of crossing the boundary at most 0.05 when the rate of allergic symptoms is equal to the acceptable rate of 10%.

Cumulative early stopping rule for allergic symptoms to NAC with 10% as the maximum allowable rate of allergic symptoms.

Number	1	2	3	4	5	6	7	8	9	10	11	12	13	14	15	16	17	18
who have completed at least one Part Boundary,	-	2	3	3	3	3	4	4	4	4	4	4	5	5	5	5	5	6
bn																		

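### The NAC allergy stopping rule counts reactions to NAC but defines n by the Part 1 infusion, so n does not match the NAC exposures for which the printed boundary holds its 5%

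*Combined protocol and SAP*

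**What the plan says.** Section 7.5 monitors allergic symptoms that require early stopping of the infusion.

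- **Numerator.** A reaction on saline is recorded as a placebo reaction, and "that participant will not be counted towards the cumulative number of participants with allergic symptoms to NAC". A reaction on NAC counts if the DSMB judges it likely related to NAC.
- **Denominator.** The count is compared with the "boundary number (bn) out of n participants who have completed at least the Part 1 infusion". Nothing restricts n to people who have had NAC.
- **Calibration.** The boundary is described as Pocock-type, and it "yields the probability of crossing the boundary at most 0.05 when the rate of allergic symptoms is equal to the acceptable rate of 10" per cent. Values of bn are printed for n = 1 to 18.

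The design is a two-period crossover with "two 2-day intervention visits separated by approximately 8 weeks" (2.1), and Section 5 gives the other treatment in Part 2. Section 4.3 makes the pharmacy responsible for "implementing the randomization order in which participants are given NAC or saline" and states no ratio or blocking. Under 3.4.1, a participant whose infusion is stopped for allergic symptoms "will be withdrawn from the study at the time the infusion is stopped".

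**The concern.** The numerator and the denominator describe different groups. A saline-first participant enters n at Part 1 but cannot contribute a reaction to NAC until about 8 weeks later. Until then that person can raise the number of reactions needed to stop, without having been at risk.

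The word *completed* adds a second problem. A NAC recipient whose Part 1 infusion is stopped is withdrawn at that moment, so on a literal reading that person never completed Part 1 and is not in n, although the reaction is in the numerator.

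The same data can therefore lead to different stopping decisions, depending on how the DSMB counts n. What is at stake is how readily the rule responds to an excessive reaction rate and, on the literal reading, whether the stated 5% holds.

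**Working it through.** **1. Reproduce the stated 5%.** Inputs from 7.5: bn = (–, 2, 3, 3, 3, 3, 4, 4, 4, 4, 4, 4, 5, 5, 5, 5, 5, 6) for n = 1 to 18, and a reaction rate p = 0.10. Let each unit of n be one NAC exposure, and let P(n, k) be the probability of k reactions after n exposures with no crossing so far. Then P(n, k) = (1 − p)·P(n − 1, k) + p·P(n − 1, k − 1), and all probability at k ≥ bn is removed and added to the crossing total.

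- n = 2: 0.1 × 0.1 = 0.0100.
- n = 3: at most one reaction can be carried forward from n = 2, so three cannot be reached; nothing is added.
- n = 4: one reaction in the first two (2 × 0.1 × 0.9 = 0.18), then two more: 0.18 × 0.01 = 0.0018. Total 0.0118.
- Continued to n = 18: **0.0474**.

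This agrees with the stated limit. The same recursion gives 0.178 at 16%, 0.310 at 20% and 0.667 at 30%. The printed values are sound when n counts NAC exposures.

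**2. Direction if reactors stay in n.** Everyone exposed to NAC has also had a Part 1 infusion, so n as written is never below the number exposed. The printed bn never falls as n rises, and the numerator is the same. The rule as written can therefore stop later than, or at the same time as, a rule based on exposures, and never earlier. Example: two NAC and two saline Part 1 infusions, and both NAC recipients react.

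| Definition | Reactions | n | bn | Decision |
|---|---|---|---|---|
| As written, reactors kept | 2 | 4 | 3 | continue |
| NAC exposures | 2 | 2 | 2 | stop |

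**3. Size if reactors stay in n.** The crossover was simulated with 18 participants, 9 per order, Part 2 at 8 weeks, reactors withdrawn and the boundary checked after each infusion (15,000 to 20,000 trials per setting). Other inputs:

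- *Reaction rate.* Section 1.5 cites 10 + 16 + 2 = 28 of 180, about 16%, for reactions of any severity. Rates of 20% and 30% are assumptions.
- *Enrolment gap.* No rate for healthy volunteers is given. Section 1.4 reports two other studies: "30 subjects enrolled over 3 years" (156 weeks / 30 = 5.2 weeks), and 11 + 9 + 11 = 31 people over 18 months (78 weeks / 31 = 2.5 weeks). Shorter gaps are assumptions.

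Probability of stopping:

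| True rate | Gap 0.5 wk | 1 wk | 2.5 wk | 5.2 wk | n = NAC exposures |
|---|---|---|---|---|---|
| 10% | 0.01 | 0.01 | 0.03 | 0.04 | 0.047 |
| 16% | 0.07 | 0.09 | 0.13 | 0.16 | 0.178 |
| 20% | 0.15 | 0.18 | 0.24 | 0.28 | 0.310 |
| 30% | 0.48 | 0.52 | 0.60 | 0.64 | 0.667 |

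At 16% and gaps of 2.5 to 5.2 weeks, the rule as written allows on average 0.2–0.5 more NAC exposures. At an 8.5-week gap, where each participant finishes Part 2 before the next starts, the two definitions give identical results.

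**4. If participants stopped early are left out of n.** Four NAC exposures with two reactors and two completers give n = 2, bn = 2 and a stop; by exposure n = 4, bn = 3 and the trial continues. In simulation at 30%, this reading stopped earlier than the exposure-based rule in about 17% (2.5-week gap) to 29% (5.2-week gap) of trials. At the acceptable 10% rate, crossing was about 0.04–0.05 at gaps of 0.5–1 week, and about 0.06–0.07 at 2.5–5.2 weeks.

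**The case against.** The best defence is that 7.5 promises only a crossing probability of at most 0.05 at 10%. With reactors kept in n that promise holds, and the documents state no sensitivity at 20% or 30%. This is correct: on that reading no stated property fails, and the shortfall is measured against the same table read by exposure. It does not settle the matter, because 7.5 gives the rule's purpose as halting accrual at an excessively high rate, and because on the literal reading of *completed* the 5% can be exceeded.

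A second defence is that the DSMB is unblinded, includes the study statistician and the investigational pharmacist, and reviews at least monthly and within two weeks of a stopped infusion with a reported event. Each reactor is also withdrawn. This stands and limits the harm. The board could count exposures, but 7.5 does not tell it to.

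A third is that the largest effects come from unsupported inputs. This also stands. With a 0.5-week gap and a 30% rate, the rule as written stops later, or never, where the exposure-based rule stops in 0.63 of trials, with 3.4 extra exposures on average. Nothing in the documents supports that combination. The 16% covers any severity, so it is probably above the rate of reactions that stop an infusion.

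A reader might also take "We intend to enroll 18 individuals to obtain the complete data sets from 15 participants" to mean that three people will be lost between Parts and that the saline-first among them will stay in n unexposed. The sentence gives no cause or timing for the losses, and 6.1 allows further recruitment to reach 15 completers, so no figure here rests on it.

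**Conclusion.** The mismatch is real and should be fixed as a matter of definition. The printed boundary meets its 5% when n counts NAC exposures, and 7.5 defines n otherwise. If reactors stay in n, which the phrase counting reactions out of n participants makes likelier, the rule can stop later or less often: about 0.13–0.16 against 0.18 at 16%, and about 0.60–0.64 against 0.67 at an assumed 30%, at gaps of 2.5 to 5.2 weeks. The loss grows with faster accrual and vanishes if each participant finishes Part 2 before the next begins. These sizes assume a 9/9 order and immediate checking after each infusion.

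Three stronger conclusions might be inferred, and the documents support none of them.

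- *The rule is always too lax.* This fails if participants stopped early are left out of n; the rule can then stop earlier and cross at about 0.06–0.07 at 10%.
- *The printed table is miscalculated.* It reproduces at 0.047.
- *Reactions to NAC go unmonitored.* The unblinded DSMB review is specified in 7.5.

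**What to change.** In the 7.5 text and in the table label, define n once as participants who have started a NAC infusion in either Part, including those whose infusion was stopped early. The printed values then meet the stated 5% through n = 18 at any accrual speed, and the ambiguity over *completed* disappears. (The table label is broken in the text available, so the point does not rest on it, but it should carry the same definition.)

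The cost is a sentence and a label; the DSMB already has the treatment assignments it needs. The downside is a slightly higher chance of stopping at the acceptable 10% rate than with reactors kept in n as written (0.047 against about 0.01–0.04), still within 5%.

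A minor addition: 6.1 allows further recruitment, and the table ends at 18. If n can go beyond 18, the statistician should extend the table. Carrying bn = 6 forward gives 0.0488 at n = 20 but 0.0503 at n = 21.

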7.6 Medical Monitoring

It is the responsibility of the Principal Investigator to oversee the safety of the study at his/her site. This safety monitoring will include careful assessment and appropriate reporting of adverse events as noted above, as well as the construction and implementation of a site data and safety-monitoring plan (see section 9 Auditing, Monitoring and Inspecting). Medical monitoring will include a regular assessment of the number and type of serious adverse events.

7.6.1 Internal Data and Safety Monitoring Board

We have formed a DSMB that will consists of the study statistician [name], endocrinologist [name] (chair), endocrinologist [name] from the University of Virginia, and investigational pharmacist [name]. They will review the data collected at each experiment on a monthly basis and more frequently if adverse events are reported (as described above in 7.5). In addition, we will file an IND with the FDA for the use of N-acetyl cysteine for the purpose outlined in this application. Past INDs filed by [name] for the IV use of N-acetyl cysteine in the study of neurological disease were given an exempt status so we anticipate the FDA will give the IND for this study and exempt status as well, but if not it will be monitored by the staff of

CONFIDENTIAL

the Clinical and Translational Sciences Institute at the University of Minnesota. They have extensive experience with the monitoring of investigator-initiated trials at the University of Minnesota, including for [name] who recently completed trial of naltrexone as a therapy for hypoglycemia unawareness in type 1 diabetes. Adverse events will be filed with the University of Minnesota IRB according to requirements.

8 Data Handling and Record Keeping

8.1 Confidentiality

Information about study subjects will be kept confidential and managed according to the requirements of the Health Insurance Portability and Accountability Act of 1996 (HIPAA). Those regulations require a signed subject authorization informing the subject of the following:

- What protected health information (PHI) will be collected from subjects in this study
- Who will have access to that information and why
- Who will use or disclose that information
- The rights of a research subject to revoke their authorization for use of their PHI.

In the event that a subject revokes authorization to collect or use PHI, the investigator, by regulation, retains the ability to use all information collected prior to the revocation of subject authorization. For subjects that have revoked authorization to collect or use PHI, attempts should be made to obtain permission to collect at least vital status (i.e. that the subject is alive) at the end of their scheduled study period.

8.2 Source Documents

Source data is all information, original records of clinical findings, observations, or other activities in a clinical trial necessary for the reconstruction and evaluation of the trial. Source data are contained in source documents. Examples of these original documents, and data records include: hospital records, clinical and office charts, laboratory notes, memoranda, subjects' diaries or evaluation checklists, pharmacy dispensing records, recorded data from automated instruments, copies or transcriptions certified after verification as being accurate and complete, microfiches, photographic negatives, microfilm or magnetic media, x-rays, subject files, and records kept at the pharmacy, at the laboratories, and at medico-technical departments involved in the clinical trial.

Data generated by the methods described in the protocol will be recorded in the subjects' medical records and/or study progress notes. Data may be transcribed legibly on CRFs supplied for each subject or directly inputted into an electronic system or any combination thereof.

8.3 Case Report Forms

The study case report form (CRF) is the primary data collection instrument for the study. All data requested on the CRF must be recorded. All missing data must be explained.

CONFIDENTIAL

If a space on the CRF is left blank because the procedure was not done or the question was not asked, write "N/D". If the item is not applicable to the individual case, write "N/A". All entries should be printed legibly in black ink. If any entry error has been made, to correct such an error, draw a single straight line through the incorrect entry and enter the correct data above it. All such changes must be initialed and dated. DO NOT ERASE OR WHITE OUT ERRORS. For clarification of illegible or uncertain entries, print the clarification above the item, then initial and date it.

8.4 Records Retention

It is the investigator's responsibility to retain study essential documents for at least 6 years after the last approval of a marketing application in their country and until there are no pending or contemplated marketing applications in their country or at least 6 years have elapsed since the formal discontinuation of clinical development of the investigational product. These documents will be retained for a longer period if required by an agreement with the sponsor. In such an instance, it is the responsibility of the sponsor to inform the investigator/institution as to when these documents no longer need to be retained.

9 Study Monitoring, Auditing, and Inspecting

9.1 Study Monitoring Plan

This study will be monitored according to FDA/GCP guidelines. The investigator will allocate adequate time for such monitoring activities. The Investigator will also ensure that the monitor or other compliance or quality assurance reviewer is given access to all the above noted study-related documents and study related facilities (e.g. pharmacy, diagnostic laboratory, etc.), and has adequate space to conduct the monitoring visit.

9.2 Auditing and Inspecting

The investigator will permit study-related monitoring, audits, and inspections by the IRB, the sponsor, government regulatory bodies, and University compliance and quality assurance groups of all study related documents (e.g. source documents, regulatory documents, data collection instruments, study data etc.). The investigator will ensure the capability for inspections of applicable study-related facilities (e.g. pharmacy, diagnostic laboratory, etc.).

Participation as an investigator in this study implies acceptance of potential inspection by government regulatory authorities and applicable University compliance and quality assurance offices.

10 Ethical Considerations

This study is to be conducted according to US and international standards of Good Clinical Practice (FDA Title 21 part 312 and International Conference on Harmonization guidelines), applicable government regulations and Institutional research policies and procedures.

CONFIDENTIAL

This material is the property of the University of Minnesota. Do not disclose or use except as authorized in writing by the study sponsor

This protocol and any amendments will be submitted to a properly constituted independent Institutional Review Board (IRB), in agreement with local legal prescriptions, for formal approval of the study conduct. The decision of the IRB concerning the conduct of the study will be made in writing to the investigator and a copy of this decision will be provided to the sponsor before commencement of this study. The investigator should provide a list of IRB members and their affiliate to the sponsor.

All subjects for this study will be provided a consent form describing this study and providing sufficient information for subjects to make an informed decision about their participation in this study. The consent form will be submitted with the protocol for review and approval by the IRB for the study. The formal consent of a subject, using the IRB-approved consent form, must be obtained before that subject is submitted to any study procedure. This consent form must be signed by the subject or legally acceptable surrogate, and the investigator-designated research professional obtaining the consent.

11 Study Finances

11.1 Funding Source

This study is funded by the Juvenile Diabetes Research Foundation.

11.2 Conflict of Interest

Any investigator who has a conflict of interest with this study (patent ownership, royalties, or financial gain greater than the minimum allowable by their institution, etc.) must refer to the Regents Policies on Individual Conflict of Interest Policy or Institutional Conflict of Interest Policy. These policies require University Faculty and staff to report external professional activities and business and significant financial interests related to his or her University activities by submitting a REPA (Report of External Professional Activities) at least once per year. Faculty and staff should also file a REPA when substantial changes in business or financial interests occur, when an activity that presents a potential conflict of interest is anticipated, or when submitting an application for research support or technology transfer, submitting research protocols to the IRB, or receiving financial contributions. All University of Minnesota investigators will follow the University conflict of interest policy.

